#### 4.5. Exploratory Analyses

As a result of comments and discussion on Version 1.0 of this SAP from the FDA prior to database lock, the following analyses will be included as exploratory analyses.

##### 4.5.1. Difference in Predicted Proportion of Remaining Function Standardized to that Predicted by the Reference Standard ( $^{133}\text{Xe}$ Scintigraphy)

To standardize each patient's results, predicted remaining function will be expressed as the difference between  $^{129}\text{Xe}$  MR and  $^{133}\text{Xe}$  scintigraphy predicted proportion of remaining function divided by the  $^{133}\text{Xe}$ -predicted proportion of remaining function. The two-sided 95% CI for the mean difference will be estimated and presented as described for the primary endpoint.

##### 4.5.2. Patient-Level Equivalence between $^{129}\text{Xe}$ MR-Predicted Remaining Function and $^{133}\text{Xe}$ Scintigraphy-Predicted Remaining Function

To evaluate the equivalence of the scan methods on a patient level, the proportion of patients will be reported whose difference in scan-predicted proportion of remaining function from  $^{129}\text{Xe}$  MRI vs  $^{133}\text{Xe}$  scintigraphy exceeds the equivalence margin (-14.7%, +14.7%). These results will also be presented using each of the ranges specified in [Section 4.1.3](#).

#### 4.6. Safety Analyses

All safety analyses will be performed on the Safety Analysis Set. Safety data, where presented by treatment, will be summarized on an "as treated" basis using descriptive statistics (e.g., n, mean, SD, median, minimum, and maximum for continuous variables; n [%] for categorical variables). Safety variables include AEs and change from baseline in vital signs and  $\text{SpO}_2$ .

##### 4.6.1. Adverse Events

The AE verbatim descriptions (investigator terms from the eCRF) will be classified into standardized medical terminology using the MedDRA. AEs will be coded to the MedDRA (Version 20.1) lower level term closest to the verbatim term. The linked MedDRA PT and primary SOC are also captured in the database.

Per CRF design, all reported AEs are treatment-emergent adverse events (TEAEs) and will be included in summary tables. An overview of the TEAEs will be summarized by treatment sequence and overall, including the number and percentage of subjects who experience TEAEs, serious TEAEs, study drug-related TEAEs, TEAEs by maximum severity, and TEAEs leading to

death or to discontinuation from study treatment. This and similar summaries will be provided by treatment sequence because the washout period between scans is generally short, and the hypothetical lag period between a scan and an AE potentially associated with drug product is of unknown duration.

The number and percentage of subjects with TEAEs will be summarized by SOC and PT for each treatment sequence and overall. A subject will be counted only once within a SOC and PT, even if the subject experienced more than one TEAE within that specific SOC and PT.

The number and percentage of subjects with TEAEs will be summarized by maximum severity (mild, moderate, or severe). If severity is missing, the TEAE will be regarded as severe.

The number and percentage of subjects with TEAEs will be summarized by causality to study drug (related/unrelated). AEs recorded as being related to study drug includes all AEs marked as having a reasonable possibility of being related to the study drug. AEs recorded as being unrelated to study drug includes all AEs marked as having no reasonable possibility of being related to study drug. If causality is missing, the TEAE will be regarded as related to study drug.

In addition to the TEAE summaries by relationship to study drug, the number and percentage of subjects with TEAEs will be summarized by the relationship to scan procedure ( $^{129}\text{Xe}$  or  $^{133}\text{Xe}$ ), as judged by investigator.

The number and percentage of subjects with TEAEs leading to death will be summarized by SOC and PT for each treatment sequence and overall. A subject data listing of all TEAEs leading to death will also be provided.

The number and percentage of subjects with serious TEAEs will be summarized by SOC and PT for each treatment sequence and overall. A subject data listing of all serious TEAEs will also be provided.

The number and percentage of subjects with TEAEs leading to discontinuation from study treatment will be summarized by SOC and PT for each treatment sequence and overall. A subject data listing of all TEAEs leading to discontinuation from study treatment will also be provided.

The number and percentage of subjects with a subjective sensation of residual anesthesia (e.g., lightheadedness, loss of sensation or awareness, loss of memory, or unconsciousness) will be summarized by PT for each treatment sequence and overall. Any such AEs related to subjective sensation of residual anesthesia will be identified by the sponsor and medical monitor prior to unblinding.

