#### 6.7. Spirometry Evaluation of FEV1

Pulmonary function will be evaluated by measuring FEV1 using spirometry prior to imaging on Day 1 (Imaging Period). For the sub-set of subjects undergoing surgery, FEV1 will also be measured during the Post-op Follow-up Period.

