#### 6.10.2. Adverse Event Reporting Period

The AE reporting period for this study begins upon receiving the first dose of study treatment during the Imaging Period and ends during the Imaging Follow-up Period. If a subject experiences an AE after signing the informed consent, but prior to receiving study drug, the event will NOT be collected unless the investigator feels the event may have been caused by a protocol procedure. Likewise, if a subject experiences an AE during the Post-Op Follow-up Period, the event will NOT be collected unless the investigator feels the event may have been caused by a protocol procedure.

All AEs (both serious and non-serious) must be assessed through the Imaging Follow-up Period. All measures required for AE management and the ultimate outcome of the AE must be recorded in the eCRF and reported to the Sponsor. All study-drug related AEs must be followed until resolution, the return to baseline, or until the event is deemed stable or irreversible.

In addition, any known untoward event that occurs subsequent to the AE-reporting period that the investigator assesses as related to the study drug should also be reported as an AE and must be recorded in the eCRF.

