#### 6.10.3. Recording Adverse Events

When an AE/SAE occurs, it is the responsibility of the Investigator to review all documentation (e.g. hospital progress notes, laboratory, and diagnostic reports) relative to the event. The Investigator will then record all relevant information regarding an AE/SAE in the eCRF. All details of any treatments initiated due to the AE should also be recorded in the subjects' notes and the eCRF.

All AEs will be documented in the appropriate section of the eCRF. Among these AEs, all SAEs (refer to [Section 6.10.1.2](#)) will be additionally documented in an SAE Report. The following will be recorded for each event on the eCRF:

- A description of the AE in medical terms, not as reported by the subject. Whenever possible, a diagnosis should be given when signs and symptoms are due to common etiology (e.g., cough, runny nose, sneezing, sore throat, and head congestion should be reported as “upper respiratory infection”).
- The date of onset (start date).
- The date of resolution (stop date).
- The severity as assessed by the investigator according to the definitions in [Section 6.10.4](#).
- The causal relationship to study drug as assessed by the investigator; the decisive factor in the documentation is the temporal relation between the AE and the study drug (refer to [Section 6.10.5](#)).

- Action taken for study drug (none, study drug discontinued, study drug dose reduction, study drug delayed).
- Other action(s) taken (none, concomitant medication given, new or prolonged hospitalization, procedural surgery).
- The outcome according to the following definitions:
  - Recovered with sequelae;
  - Recovered without sequelae;
  - Ongoing, no therapy;
  - Ongoing, therapy;
  - Died, or
  - Change in toxicity grade/severity.
- Serious Adverse Event (as defined in [Section 6.10.1.2](#)): yes or no.

If, in any subject, the same AE occurs on several occasions (unless the AE is continuous and of stable grade), then the AE in question will be documented and assessed each time. For an SAE, the information listed above to be recorded in the eCRF will also be recorded in the SAE Report. Only AEs that fulfill the criteria for SAEs (refer to [Section 6.10.1.2](#)) should be recorded in the SAE Report.

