### 8.8. Safety Analysis

All safety analyses will be performed on the Safety population, unless otherwise stated.

AEs will be coded using MedDRA terminology. Events are defined as AEs if they start or worsen after a subject's administration of study drug. All AEs will be summarized by SOC, preferred term, severity and relationship to study drug. AEs leading to death or to discontinuation from study drug and SAEs will also be tabulated. In the by-subject summary, a subject having the same event more than once will be counted only once and by greatest severity.

Vital signs, including change from baseline, will be summarized.

Prior and concomitant medications will be coded using the World Health Organization (WHO) Drug dictionary. Concomitant medications will be summarized descriptively. The summary tables will show the number and percentage of subjects by preferred term. Subjects who take the same medication (in terms of the preferred term) more than once will only be counted once for that medication. Prior and concomitant medications will be listed separately.

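### SAP 4.6.1 counts every reported AE as treatment-emergent with no onset test, although the protocol collects some procedure-related AEs before the first dose; the effect depends on the CRF

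*SAP*

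**What the plan says.** SAP 4.6.1 settles treatment emergence in one sentence: "Per CRF design, all reported AEs are treatment-emergent adverse events (TEAEs) and will be included in summary tables". All the AE tables that follow (overview, by system organ class and preferred term, severity, causality, serious events, discontinuations) build on it. The section adds two missing-data rules. An event with no severity is taken as severe, and for relationship the rule is "If causality is missing, the TEAE will be regarded as related to study drug".

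The protocol has two relevant provisions.

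- Protocol 6.10.2 sets the regular window: "The AE reporting period for this study begins upon receiving the first dose of study treatment during the Imaging Period", with its end in the Imaging Follow-up Period. It then makes an exception for AEs in the interval from consent to dosing: "prior to receiving study drug, the event will NOT be collected unless the investigator feels the event may have been caused by a protocol procedure". A parallel exception covers the Post-Op Follow-up Period.
- Protocol 8.8 fixes which events are analysed: "Events are defined as AEs if they start or worsen after" administration of study drug.

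SAP Section 9, which lists changes from the protocol, has no entry on AEs.

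**The concern.** A pre-dose AE attributed to a protocol procedure is collected under Protocol 6.10.2, lies outside the definition in Protocol 8.8, and is a TEAE under SAP 4.6.1. For that event the plan gives two different answers, and the one written in the SAP is the one that will be programmed.

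The study does have procedures before dosing. Spirometry is done on Day 1 before imaging (Protocol 6.7), and women of childbearing potential have blood drawn at Screening (Protocol 6.5). Lightheadedness after spirometry, for instance, would be a TEAE by rule. It is also one of the named examples of residual anesthesia, the AE of special interest, so only the judgement of the sponsor and medical monitor would keep it out of that table.

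Safety and tolerability of the gas is a stated secondary objective, and SAP 4.6.1 reports TEAEs by treatment sequence, where the groups are small. An event that preceded both gases does not belong in those rates.

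**Working it through.** The documents give no AE rate and no count that depends on this rule, so there is no stated figure to reproduce. The check compares the texts and then scales the effect by simple proportion.

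**Step 1: how each text treats the possible events in a subject who is later dosed.**

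| Event | Collected under Protocol 6.10.2? | Analysed AE under Protocol 8.8? | TEAE under SAP 4.6.1 if reported? |
|---|---|---|---|
| Before first dose, not attributed to a procedure | No | No | Does not arise |
| Before first dose, attributed to a procedure | Yes | No, unless it worsens after dosing | Yes |
| From first dose to Imaging Follow-up | Yes | Yes | Yes |
| Post-op period, attributed to a procedure | Yes | Yes, onset is after dosing | Yes |

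Only the second row conflicts.

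**Step 2: can such an event reach the tables?** Three conditions must hold. The investigator must attribute the event to a protocol procedure. The subject must later receive at least one gas, because safety is analysed on the Safety Analysis Set (SAP 4.2.1). The CRF must have a place to record the event. The CRF is not among the documents. The Schedule of Events marks AEs at Imaging and Imaging Follow-up only, but Imaging includes the pre-dose spirometry, so the schedule does not exclude a pre-dose AE on Day 1.

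**Step 3: size per event.** Inputs: 32 planned completers (Protocol 3.1) and 1:1 allocation to two sequences (SAP 1.3). Assumption: 32 subjects dosed, so 32/2 = 16 per sequence. For k subjects whose only AE is pre-dose, all in one sequence:

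- overall excess = k/32
- excess in that sequence = k/16

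| k (assumed) | Overall | In that sequence |
|---|---|---|
| 1 | 1/32 = 3.1 points | 1/16 = 6.3 points |
| 3 | 3/32 = 9.4 points | 3/16 = 18.8 points |

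The range for k is illustrative. With an onset-based rule the excess is 0. The Safety Analysis Set includes anyone dosed once, so with replacements it may exceed 32, and each figure would then be smaller.

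**Step 4: the drug-related count.** A pre-dose event enters it only if the investigator marks the event as related or if causality is missing. Otherwise it raises the TEAE rate alone.

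**Step 5: can dates separate the events?** Protocol 6.10.3 lists an onset date for the eCRF and no onset time. Spirometry and dosing can fall on the same day, and Screening and Imaging may share a day. A date comparison cannot place a same-day event before or after the dose.

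**The case against.** The strongest reply is that the SAP sentence describes the CRF. If the AE form accepts only post-dose events, the sentence already carries out Protocol 8.8 and nothing is inflated. The Schedule of Events, with no AE assessment at Screening, leans that way. This stands as far as it goes: a reader might infer that TEAE rates will be inflated, and the documents do not establish that. But in that case the CRF has no place for events that Protocol 6.10.2 says are collected, so the mismatch moves rather than disappears.

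Four further limits are fair.

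- **Post-op events.** Because Protocol 6.10.2 applies the same condition after surgery ("the event will NOT be collected unless the investigator feels the event may have been caused by a protocol procedure"), a reader might infer that these events are misclassified too. They are not. In a dosed subject they start after dosing, so they satisfy Protocol 8.8 and any onset-based TEAE definition.
- **Attribution to the gas.** A reader might infer that pre-dose events will be charged to the drug. Protocol 6.10.5 requires the investigator to record relationship to study drug, so a blank field should be rare. Treating a blank as related is a conservative choice, not an error.
- **Share of the observed rate.** Protocol 1.5 reports no TEAEs in 103 exposed people, and a reader might infer that one misclassified event would dominate the result. No document gives an expected rate for this trial or for pre-dose events, so that cannot be supported.
- **Direction.** Counting pre-dose events overstates TEAEs. It cannot hide harm from the gas.

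**Conclusion.** The contradiction between SAP 4.6.1 and Protocol 6.10.2 and 8.8 is real for one class of event: procedure-related AEs between consent and first dose in subjects who are then dosed. Whether it distorts the safety tables depends on a CRF that the documents do not show. If the CRF records these events, the cost is 3.1 points overall and 6.3 points in the affected sequence for each subject with no other AE, on the assumption of 32 dosed subjects split equally. If it does not, the TEAE rates stand and the CRF falls short of the protocol. Either way the texts need to be reconciled. The route is narrow and few such events are to be expected, so the point is minor. It is worth making because the correction is specific and cheap.

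**What to change.** 1. Replace the sentence in SAP 4.6.1 with: a TEAE is an AE that starts or worsens at or after the first dose of either gas. Naming either gas matches the Safety Analysis Set. SAP 4.2.7 already uses the first dose of study product to separate prior from concomitant medications, so the anchor is not new.
2. List pre-dose procedure-related AEs separately and leave them out of TEAE incidence.
3. Apply the missing-severity and missing-causality rules to TEAEs only.
4. Keep post-op procedure-related AEs as TEAEs. They may be shown separately, but there is no ground of onset for excluding them.
5. Check the CRF against Protocol 6.10.2. If it cannot take pre-dose events, bring the two into line.

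The cost is a derived flag in the AE dataset, plus an onset time or an investigator's pre-/post-dose indicator for events on the dosing day. A change of SAP wording alone is not enough, because the listed eCRF fields give only an onset date. Sample size and the efficacy analyses are not affected.

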### 4.3. Exclusion Criteria

Subjects will not be eligible for participation in the study if they meet ANY of the following criteria:

1. Baseline blood oxygen saturation ( $\text{SpO}_2$ )  $< 90\%$  at rest (refer to [Section 6.3.2](#)). For patients requiring routine supplemental oxygen,  $\text{SpO}_2$  measurements should be taken with the patient's normal oxygen supplementation.

2. Female subjects of childbearing potential with a positive serum pregnancy test at screening, or who are not taking (or not willing to take) acceptable birth control measures through the Follow-up Period. Adequate birth control methods include with a monogamous partner who was sterilized more than 6 months prior to screening, or measures with a Pearl index of  $<1$  used consistently and correctly (including intrauterine devices, or implantable, injectable, oral, or transdermal contraceptives). Women are not considered to be of childbearing potential if they meet at least 1 of the following 2 criteria as documented by the Investigator:
  - They have had a hysterectomy, bilateral salpingectomy, or bilateral oophorectomy at a minimum of 1 menstrual cycle prior to signing the ICF; or
  - They are post-menopausal: for women  $\geq 55$  years of age, defined as  $\geq 1$  year since their last menstrual period, or for women  $< 55$  years of age, defined as  $\geq 1$  year since their last menstrual period and have a follicle-stimulating hormone (FSH) level in the laboratory's normal range for post-menopausal phase.
3. Women who are lactating and insist on breast feeding.
4. Subjects who have received any other investigational therapy within 4 weeks prior to Screening.
5. Subjects who require anesthesia or heavy sedation to undergo MRI testing. Mild sedation could be acceptable (i.e. a low dose oral acting anxiolytic medication such as alprazolam) as long as, in the opinion of the investigator, the subject meets Inclusion Criteria #4 and #5.

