#### 6.6. MRI-suitable Screening

As indicated in exclusion criteria #5 ([Section 4.3](#)), a subject who requires anesthesia or heavy sedation in order to undergo MRI testing cannot participate in this study. However, mild sedation (i.e. a low dose oral acting anxiolytic medication such as alprazolam) could be acceptable if, in the investigator's opinion, the subject is still able to comply with all study procedures.

There are no additional protocol specific requirements or restrictions with respect to a subject being suitable for MRI testing.

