#### 6.10.1.1. Adverse Events of Special Interest

Subjective sensation of residual anesthesia (e.g., lightheadedness, loss of sensation or awareness, loss of memory, or unconsciousness) is an AE of special interest for this study. The next dose of any study treatment will not be administered until any sensation of residual analgesia has resolved. If the subject has received their last dose, they will be observed until the sensation of residual analgesia has resolved.

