### 1.3. Randomization and Blinding

All randomized subjects will be divided between 2 treatment sequences in a 1:1 ratio. Subjects will be randomized to receive either  $^{129}\text{Xe}$  followed by  $^{133}\text{Xe}$ , or  $^{133}\text{Xe}$  followed by  $^{129}\text{Xe}$ . All subjects will receive at least 1 dose of hyperpolarized  $^{129}\text{Xe}$  and 1 dose of  $^{133}\text{Xe}$  during study participation.

This is an open-label study. Images generated from this study will be interpreted by a trained central reader, blinded to the subject's medical history and all study assessments. The images will be uploaded in a blinded manner to a computer for review. Both  $^{133}\text{Xe}$  scintigraphy and hyperpolarized  $^{129}\text{Xe}$  MRI will be quantified using commercially available software.

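### The residual-anesthesia events are selected without masking or a preferred-term rule, and no planned table shows whether an anxiolytic given for the MRI contributed to the count

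*SAP*

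**What the plan says.** **The event.** Protocol 6.10.1.1 states: "Subjective sensation of residual anesthesia (e.g., lightheadedness, loss of sensation or awareness, loss of memory, or unconsciousness) is an AE of special interest". The symptoms are examples, not a closed list.

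**How it is counted.** SAP 4.6.1 tabulates these events by preferred term, for each treatment sequence and overall. Selection is described in one sentence: "Any such AEs related to subjective sensation of residual anesthesia will be identified by the sponsor and medical monitor prior to unblinding".

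**Masking.** SAP 1.3 states: "This is an open-label study". Protocol 3.2 says that the procedures cannot be blinded. Protocol 5.5 and SAP 1.3 describe blinding for central image reading only. SAP 4.6.1 also summarizes adverse events by the investigator's judgement of relationship to the 129Xe or 133Xe procedure, so that attribution is part of the data.

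**Sedation.** Exclusion criterion 5 (Protocol 4.3) and Protocol 6.6 rule out anesthesia or heavy sedation for the MRI, but "mild sedation (i.e. a low dose oral acting anxiolytic medication such as alprazolam) could be acceptable". There is no matching provision for scintigraphy.

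**The hold on further dosing.** Protocol 6.10.1.1 names the event as residual anesthesia and then says: "The next dose of any study treatment will not be administered until any sensation of residual analgesia has resolved". Footnote 8 of Appendix 1 refers back to the sensation of residual anesthesia.

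**The concern.** Selecting events before unblinding protects a count when the people selecting do not know the treatment. Here nothing is masked from them, and there is no written rule to limit their discretion. Two reasonable people could include different events and so report different counts for the trial's only named event of special interest. Safety is the first-listed secondary objective.

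The sedation provision adds a second question. An anxiolytic taken in order to undergo MRI is tied to the 129Xe scan. The documents call its effect sedation, and the event's examples include reduced awareness: "lightheadedness, loss of sensation or awareness, loss of memory, or unconsciousness". Protocol 1.4 describes xenon itself as an anesthetic. A reader of the planned table could not tell whether an event occurred in a sedated subject. A sedative effect might be read as a xenon effect, or a xenon effect put down to the sedative.

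**Working it through.** No figure in the plan can be reproduced here. The documents give no expected rate of residual anesthesia, no expected share of sedated subjects and no precision target for safety. The check is mainly of the text.

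**1. What the selection step protects.** SAP section 1 uses unblinding for the opening of the study database. Read that way, SAP 4.6.1 requires events to be selected before results are summarized. That is protection by timing. For masking, the sponsor and medical monitor would have to be kept from the treatment sequence and the scan attribution. No such step is described, and SAP section 4 has all listings sorted by treatment sequence.

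**2. Whether a rule limits the selection.** Neither document gives a preferred-term list or any other selection rule, only the examples.

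**3. Whether sedation can be seen in the table.** The table is by sequence and overall. The subgroups in SAP section 6 concern the primary efficacy endpoint only. SAP 4.2.7 plans separate summaries of inhaler use and oxygen flow; sedatives have no equivalent beyond the general concomitant-medication tables.

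**4. Whether capture is the same in both orders.** Protocol 6.10.2 generally does not collect events before the first study dose. In the 129Xe-first order, sedative symptoms that begin before the MRI dose would mostly not be collected. In the 133Xe-first order the subject has already been dosed, so the same symptoms would be. Any sedation effect could therefore fall unequally on the two sequences being tabulated.

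**5. Illustration of size, on assumed inputs.** Let p be the true xenon event rate, s the share of subjects sedated and q the chance that sedation produces a qualifying event. If the two causes act independently,

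observed rate = 1 − (1 − p)(1 − s·q).

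With 32 subjects (the planned completers; the Safety Analysis Set may be larger because discontinued subjects are replaced):

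| s | q | p = 0: rate, count | p = 5%: rate, count |
|---|---|---|---|
| 0 | any | 0%, 0 | 5%, 1.6 |
| 10% | 10% | 1%, 0.3 | 5.9%, 1.9 |
| 20% | 30% | 6%, 1.9 | 10.7%, 3.4 |
| 30% | 50% | 15%, 4.8 | 19.3%, 6.2 |

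Example: p = 0, s = 0.20, q = 0.30 gives 1 − 1 × (1 − 0.06) = 0.06, and 32 × 0.06 = 1.92 subjects.

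The values of p, s and q are all assumptions. The table shows only how the count responds and that it includes no effect at all.

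**6. Sensitivity of a small count.** The exact (Clopper-Pearson) 95% interval is 0 to 10.9% for 0/32 and 0.8% to 20.8% for 2/32. Including or leaving out two events visibly changes the reported result.

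**The case against.** The strongest reply is that little can be lost. All reported adverse events are treated as treatment-emergent and enter the system organ class and preferred-term tables whatever their attribution (SAP 4.6.1), and all data are listed (SAP section 4). An event left out of the special-interest table is still visible under its own term. Concomitant medications are recorded (Protocol 5.6), summarized and listed (SAP 4.2.7), and weighed in the relatedness judgement (Protocol 6.10.5). Selection before the database is opened is a real protection. All of this stands, and it makes the point minor. It does not supply a rule for the special-interest table or mask those who compile it.

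A reader might infer that a 129Xe anesthesia rate is confounded. The documents do not support that. No 129Xe-specific rate of this event is planned. They do not say that a low-dose anxiolytic causes the listed symptoms; overlap is plausible from the word sedation, but no more. Anxiolytic use is optional, its frequency is unknown, and subjects must still be able to comply.

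A reader might also infer that the sponsor picks events one at a time, knowing which gas and which medication came first. Case-by-case selection is only an inference from the missing list, and the medical monitor takes part. Medication start and event onset are recorded by date (Protocol 5.6 and 6.10.3), so with same-day scans the listed fields may not show the order. What can be said is that the assessors can know the sequence and the investigator's attribution.

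**Conclusion.** The selection step gives protection by timing at most, and no masking. Without a preferred-term rule, the special-interest count depends on the judgement of people who can know the exposures. This holds whether or not anyone is sedated.

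Sedation could also contribute to the count, and no planned table separates it. Its size cannot be estimated from the documents and is zero if no subject takes an anxiolytic. It would be too strong to call the safeguard empty or the safety result uninterpretable, because the general event tables and listings remain complete.

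The wording conflict between anesthesia and analgesia in Protocol 6.10.1.1 is a separate matter and has no bearing on the counting argument. The primary endpoint is unaffected. Overall this is a minor safety-reporting correction.

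**What to change.** 1. In SAP 4.6.1, replace the selection sentence with a list of MedDRA 20.1 preferred terms mapped from the protocol's examples and approved before database lock. Suggested text: *Residual-anesthesia events are all TEAEs coded to a preferred term on the appended list, regardless of attributed cause or procedure. The list is approved before database lock.* This also replaces the reference to unblinding with database lock, a milestone that exists in an open-label trial.

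2. Using the medications already recorded, flag these events in the listing, or tabulate them, by anxiolytic or sedative use on the imaging day. Label this descriptive.

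3. Reconcile *anesthesia* and *analgesia* in Protocol 6.10.1.1 with footnote 8 of Appendix 1.

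The cost is one SAP paragraph, a short term list and one flag or extra table; no new data are needed. The drawback of the split is very small cells. A fixed list may also count some events that a clinician would set aside; these can be discussed in the narrative without changing the count. Recording the clock time of the anxiolytic is not part of this fix: it would change data collection and could not order events without an adverse event onset time as well.
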